NMES uses a lightweight, battery powered electrical stimulation unit (which is attached to the patient via self-adhesive electrodes) to produce a controlled contraction of the underlying muscle. It can be self-administered at home while the participant is passively sitting or lying down thus decreasing the demands of exercise while still allowing the participant many of the same benefits.²⁴ Previous studies using NMES and those with HF have shown benefit, but, the protocols have varied widely, the outcome variables of interest have also varied widely, in addition there was no further formal exercise program encouraged upon completion of the study. The innovation of this study is that all the previous knowledge gained has been merged into a protocol that is double blinded, patient centered protocol to improve compliance, tolerability, and ease of use. Also, this proposal focuses on NMES being used as the stepping stone to enable those with HF to participate in structured exercise program.

Section 2: Rationale and Specific Aims Research Design and Methods

The purpose of this double blinded, randomized, controlled, longitudinal study is to determine if NMES will increase muscle mass and strength, decrease sedentary time, and improve HF symptoms and exercise capacity, thus improving quality of life in patients with HF. It is hypothesized that with this increase in muscle mass, patients will improve overall exercise tolerance and capacity. In addition, after the intervention patients will be better able to tolerate an exercise program thus improving adherence to exercise recommendations. After 6 weeks of intervention, patients will be encouraged to participate in a formalized exercise program.

Specific Aim 1: Test the effect of NMES on muscle mass and strength in patients with HF. We will use DXA and dynamometer to evaluate this aim. We hypothesize that NMES will increase lean muscle mass and decrease fat mass of the thighs. Also that strength and force of the thighs will improve.

Specific Aim 2: Evaluate the effect of NMES on exercise capacity and activity in patients with HF. We will use 6-minute walk test to evaluate exercise capacity and ActivePal accelerometer to evaluate activity levels. We hypothesize that exercise capacity and the amount of daily activity will increase while sitting/lying time will decrease from pre intervention to post intervention time points.

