Specific Aim 3: Assess the effect of NMES on HF symptoms and health-related quality of life (HRQOL). We will use the Memorial Symptom Assessment Scale-HF and Minnesota Living with Heart Failure Questionnaire (MLHFQ) to evaluate this aim. We hypothesize that HRQOL will increase while HF symptoms decrease.

Specific Aim 4: Evaluate the effect of NMES on enrollment and utilization of a formalized exercise program. We hypothesize that patients in the NMES group will be more likely to participate in a formalized exercise plan following the intervention than the sham group.

We will use a double blinded, randomized controlled longitudinal study design to determine if NMES will increase muscle mass and strength, decrease sitting and lying time, and improve HF symptoms and exercise capacity thus improving likelihood of engagement with a structured exercise program. Patients will be randomized to either intervention that includes NMES or to a sham/wait list control group.

Importance of the Knowledge to be gained

Research has shown that patients with HF see significant improvement in their HF symptoms, decrease hospitalizations, and find improvement in their overall health when they follow a prescribed exercise regimen. Many patients are not willing or able to begin exercising or discontinue the exercise regimen once they do start one due to high levels of fatigue and shortness of breath due to muscle wasting that occurs with HF. Having a lower starting point (starting with passive NMES) for exercise and building muscles up before enrolling in a cardiac rehabilitation program to meet the current exercise recommendations will likely improve the success for patients in being able to exercise. It is expected that all patients will benefit from a formalized exercise program regardless of NMES or Sham randomized group.

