The data collected in this study will be used to prepare a NIH RO1 application, which will launch my independent program of research. Using NMES to improve exercise use in patients with HF is of specific interest to the NIH due to all the potential improvements previously discussed. There is a great potential for extramural funding for development of non-pharmacologic interventions that maintain/improve independence, increase quality of life, decrease hospitalizations, and improve patient outcomes. This study will add to the science by determining if NMES can be used as a stepping stone for enrollment into formalized exercise rehabilitation program, or as an approach for those who are unable to exercise.

Section 3: Inclusion and Exclusion Criteria

Inclusion criteria

Adult patients with a recent hospitalization or clinic visit for heart failure, (ICD-9 428; ICD-10 I50) and one of the following: BNP >400 OR NT-proBNP>900 (If renal dysfunction >1200) OR Echo showing myocardial remodeling, dilation, hypertrophy, or dysfunction will be included in this study. In addition patients must live at home, and not regularly exercise (10 minutes or more a day of exercise most days of the week for the past week).²⁵ Sedentary patients are the focus of this intervention because they would most likely see significant improvement with the intervention.

Exclusion criteria

Patients, who have undertaken cardiac rehab within the 12 months prior to enrollment, have a cognitive or other impairment which prevents accurate application of intervention or inability to provide informed consent, End Stage Renal Disease or receiving mechanical ventilation, receiving non-approved FDA-investigational agents or devices, has received a heart transplant, a destination Ventricular Assist Device (LVAD), pacemaker, or implantable cardiac device, previously used NMES (Neuromuscular electrical stimulation) or TENS (Transcutaneous electrical nerve stimulation) or Uncontrolled arrhythmia's or 3 degree AV heart block, are unable to correctly apply and operate the device even after instruction (as determined by the Research Assistant), those with wounds over area of proper placement of electrodes, or those who are unable to speak and write English. Women who are pregnant or planning to become pregnant.

Children will not be included in this study. Although HF can occur in all ages, it is primarily a disorder of the elderly. In addition the causes of HF in children is very different than adults.

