Section 4: Enrollment and Randomization

Patients who meet eligibility criteria will be referred to the investigator or the research assistant by cardiology, heart failure, or emergency room providers during their routine evaluation of patients eligible for participation in other heart failure research studies through the medical record system. In addition, a clinical research systems

request has been made to allow for notification to the PI the identification all heart failure patients admitted to the hospital so the PI or RA can screen for eligibility. In addition, [name] will release names and contact information for previous participants in her HF study to the PI if the participant has previously indicated they would like to be contacted for future research studies for screening to determine eligibility to participate in this study. The patient will then be contacted by a BISTRO team member for a full explanation of the study and determine interest in participating. If they are interested and are also willing to participate in the FIT Core study (IRB #170755085), an appointment for follow up discussion and possible consenting for both studies) will then be set up for the following week or two. At which time they will come to the school of nursing for final consideration, potential consenting, begin data collection.

In order to ensure that the two groups are comparable between treatment and sham interventions, the participants will be randomized according to gender. Randomization via minimization will be used in order to avoid an unbalanced number of women in the two comparison groups due to chance.²⁶ A file of the computer-generated random assignments will be kept by the research assistant so the PI/data collector remains blinded in a protected Box Health account.

Section 5: Study Procedures

Intervention and Sham/Wait List Control Conditions

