Data analysis will be done using SPSS, v. 22; an alpha level of .05 will be used for all tests except where noted. Study measures will be examined using univariate statistics, including means, standard deviations and frequency distributions, and graphical techniques, such as box plots and histograms. Distributions for continuous outcome measures will also be examined for violations of normality using normal probability plots. If there is evidence of lack of normality for a particular outcome, transformations (e.g., logarithmic) will be used so that the distribution of the transformed variable more closely approximates normality. The analysis strategy to be used to test all aims is repeated measures analysis of variance (ANOVA). Each ANOVA model will include the main effects of Time (baseline, 6 weeks, 6 months' post intervention period) and Group (intervention and sham intervention), as well as the Time by Group

interaction. Post-hoc pairwise comparisons of means will be done using Fisher least significant difference procedure. The repeated measures models will be estimated using the MIXED procedure in SAS. This analysis will: **test the effect of NMES on muscle mass and strength in those with HF (Aim 1); evaluate the effect of NMES on exercise capacity and activity (Aim 2); and assess the effect of NMES on HF symptoms and quality of life (QOL); and finally, evaluate the effect of NMES on enrollment and utilization of a formalized exercise program (aim 4).** There will be a separate model for each outcome variable, and the significance of the main and interaction effects will indicate the effect of the intervention over time.

Power Considerations

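### Aim 4 (joining and using a formal exercise programme) has no listed measure; the only item tagged to it is hospital stays, and it is assigned to an ANOVA that does not fit it

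*Combined protocol and SAP*

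**What the plan says.** Section 2 states the Aim 4 hypothesis as a comparison of arms after treatment: "patients in the NMES group will be more likely to participate in a formalized exercise plan following the intervention than the sham group". Aims 1 to 3 each name their instruments; Aim 4 names none. The passage on the importance of the knowledge to be gained says the study will add to the science by "determining if NMES can be used as a stepping stone for enrollment into formalized exercise rehabilitation program".

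Section 2 also sets when uptake can begin: "After 6 weeks of intervention, patients will be encouraged to participate in a formalized exercise program". The NMES Protocol Summary in Section 5 repeats this and gives examples of programmes that would count.

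In Section 5, Instruments and Measures, the only item carrying an Aim 4 tag is in item 7: additional hospital stays taken from the clinic record. The table of variables collects clinical data once, before treatment, and limits telephone interviews to the intervention phase.

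Section 8, Statistical Analysis, applies one method throughout: "The analysis strategy to be used to test all aims is repeated measures analysis of variance (ANOVA"). The model has "main effects of Time (baseline, 6 weeks, 6 months' post intervention period"), Group and their interaction. Aim 4 is named explicitly among the aims it serves: the analysis will "evaluate the effect of NMES on enrollment and utilization of a formalized exercise program (aim 4"). The reading rule is that "the significance of the main and interaction effects will indicate the effect of the intervention over time".

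**The concern.** An aim needs a variable, a source and a collection time, and Aim 4 has none of these in the listed measures. The item tagged to it answers another question: a hospital stay says nothing about whether a patient joined a programme. If the plan is followed as listed, the trial reaches analysis with the wrong variable for one of its four aims. Attendance at community or home programmes may be hard to reconstruct later.

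The assigned model adds a smaller difficulty. Uptake is a yes/no result that arises mainly after treatment. Recorded once, it has no Time factor. Coded at three visits, it starts near zero in both arms and rises in both.

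**Working it through.** **1. Is enrolment or use listed anywhere?**

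| Place | What it holds | Enrolment or use? |
|---|---|---|
| Section 2, Aim 4 | Hypothesis, no instrument | No |
| Section 5, 14 instruments | Body composition, strength, walking, activity, symptoms, quality of life, comorbidity, fatigue, exercise confidence and expectations, function, pain, depression | 0 of 14 |
| Section 5, variables table | 17 rows | 0 of 17 |
| Section 5, weekly calls | Adherence, tolerance, skin, equipment; intervention phase only | No; the calls end before programmes are encouraged |
| Section 5, item 7 | Hospital stays, tagged Aim 4 | Different outcome, no follow-up row |

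The nearest candidates do not substitute. The accelerometer, tagged to Aim 2, measures movement. The self-efficacy and expectation scales measure confidence and belief.

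**2. The plan's own power figures.** Inputs from Power Considerations: 27 per arm (N = 54), alpha .05, f = 0.40 or 0.25, with m = 3 visits. The within-person correlation is described only as modest, so I take 0.32 as an assumption.

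- Group: noncentrality = f²·N·m / (1 + 2 × 0.32), on 1 and 52 df. For f = 0.40: 25.92/1.64 = 15.8, power 97.4% (stated about 97%). For f = 0.25: 10.125/1.64 = 6.17, power 68.4% (stated at least 69%).
- Interaction, f = 0.25: 10.125/(1 − 0.32) = 14.9 on 2 and 104 df, power 93.6% (stated 95%).

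The statement reproduces within 2 points. It concerns ANOVA F tests over three visits and gives no figure for a comparison of two proportions.

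**3. What the ANOVA shows if Aim 4 is coded at three visits.** Take the limiting case 0, 0, Y, where Y is 1 if the patient enrolled by the final visit. Section 3 excludes regular exercisers and anyone with cardiac rehabilitation in the previous 12 months, so baseline values should be near zero.

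Example with no difference between arms, 2 of 27 enrolled in each:
- Visit means are 0, 0 and 4/54 = 0.0741; the grand mean is 0.0247.
- Time sum of squares = 54 × (2 × 0.0247² + 0.0494²) = 0.1975.
- Within-patient sum of squares = 4 × 2/3 = 2.667; error = 2.667 − 0.1975 = 2.469.
- F = (0.1975/2) / (2.469/104) = 4.16 on 2 and 104 df, p = 0.018. Group and interaction both have p = 1.0.

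Enumerating all 28 × 28 possible results, with equal assumed final rates:

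| Rate in both arms | Group significant | Time significant |
|---|---|---|
| 5% | 2.3% | 33.8% |
| 10% | 5.1% | 82.9% |
| 20% | 4.8% | 99.8% |
| 30% | 5.0% | 100% |
| 40% | 4.6% | 100% |

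Time detects that patients started programmes. Group stays at or below about 5%.

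**4. What a direct comparison offers.** The documents give no enrolment rates; all rates here are assumed.

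| Sham vs NMES | Fisher exact power | ANOVA Group power |
|---|---|---|
| 20% vs 40% | 26.3% | 36.3% |
| 20% vs 50% | 55.0% | 65.3% |
| 20% vs 60% | 80.2% | 86.7% |

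The 95% CI half-width for the difference, 1.96·√(2p(1−p)/27), is 11.6 points at p = 5%, 21.3 at 20% and 26.1 at 40%.

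**The case against.** The strongest reply is that absence from these two lists proves little, because they are visibly incomplete. The Self-Care of Heart Failure Index is in the table but not among the described instruments. Reason for drop-out and adverse events will be collected, yet neither has a table row. The REDCap forms are not supplied, and participants must be "also willing to participate in the FIT Core study", whose measures are also unseen. The ActivPAL instructions in Section 12A time the third wear from completion of cardiac rehabilitation, which suggests someone may track it. Institutional rehabilitation might also be traceable in the chart. This stands to the extent that a reader might infer enrolment will not be recorded at all, and the documents do not support that. They support only that it is not listed. The mismatched tag remains either way.

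On the model, a reader might infer that the ANOVA raises the false-positive rate for Aim 4. That is not supported. The Group term is near nominal. An uncorrected split-plot interaction test would reject in 7.5–8.4% of null cases above, but on 1 and 52 df it rejects in 2.3–5.1%, and Section 8 states no covariance structure. Nor is a Time effect a false NMES finding unless it is accepted alone. The reading rule is loose enough to allow that, but Power Considerations speaks of group differences over time, and the looseness affects every aim. Finally, the Group term has more power than Fisher's test, so power is no reason to change.

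**Conclusion.** The point holds on the text: Aim 4 has no listed measure (0 of 14 instruments, 0 of 17 rows), its only tagged item is a different outcome, and its analysis is a three-visit model in which only the between-arm contrast answers the question. The reason to change the model is interpretability. The numerical illustrations rest on assumed enrolment rates, 27 completers per arm, and participation near zero at the first two visits; the missing measure depends on none of these.

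This should be fixed, ideally before final visits begin. It ranks below an essential correction because the study is described as exploratory, no aim is named primary, Aims 1 to 3 are untouched, and unseen forms may already hold the data.

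**What to change.** - At the final visit, in both arms, record enrolment in any formal programme (yes/no), type, start date and sessions attended. Add this row to the variables table, or cite the form there if it already holds these items.
- Correct the Aim 4 tag on hospital stays in item 7.
- Take Aim 4 out of the ANOVA sentence. Report the NMES-minus-sham difference in proportions at the final visit with a 95% CI, and describe sessions attended by arm.
- State that the Power Considerations figures do not cover Aim 4.
- Reconcile the final-visit timing, since it sets the enrolment window. The protocol summary gives 3 months after treatment (about 13 weeks). The variables table and Section 10 give 6 months (26 − 6 = 20 weeks after treatment if counted from baseline). Section 8 reads as 6 months after the intervention (26 weeks). Section 12A counts 3 months from the end of rehabilitation, which has no date for a patient who never enrols. This is a separate inconsistency affecting all repeated measures and adds no weight here.

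The cost is about four questions at a visit already planned, one table row and a few sentences. Self-reported attendance carries some recall error. Power for this aim becomes visibly lower: about 80% by Fisher's test needs roughly 47% vs 10%, 60% vs 20% or 72% vs 30%.

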gentle pumping sensation is felt. Participants will direct the amount of stimulation acceptable on both thighs to improve acceptance of the modality.^{10,24,29-31} To assist better tolerance large electrodes (2x4) will be used and participants will also be instructed to be in a seated position with chair close to the wall so that their leg is 90-degree angle and then push against the wall to decrease any uncomfortable feeling during the contraction. For the Sham group, electrodes will follow the same landmarks, but the stimulation will only increase to an intermittent tingling sensation with the machine setting on TENS instead of NMES which is not enough to make noticeable changes in muscle mass or circulation.³² Participants in both groups will be given written instructions and contact information of the person (RA) to contact should there be any problems or concerns with the intervention. All participants will do a return demonstration to assure proper knowledge has been gained. Adherence to the study protocol will be determined by the amount of time the EMPI machine records that it was used, the intensities utilized along with verbal verification during the weekly phone calls.

NMES Protocol Summary

- 5 sessions per week for 6 weeks done independently at home, with 15 minutes per session (15 stimulations per day/session, 15 seconds stimulation on, 15 seconds recovery time) to both legs.
- Intervention group only: We expect the participant to develop tolerance to the treatment and thus increase the intensity of the NMES over time.
- At the end of the trial, the participants will return to have all measures repeated. Sham group will then be offered the active treatment. In previous HF studies (non-NMES) done by the mentor of this grant, no participants have accepted the offer of the intervention after completion of the sham/control so this number is expected to be very small.
- Participants will be encouraged to begin a formalized exercise plan such as Silver Sneakers, a home based cardiac rehabilitation or institutional cardiac rehabilitation program.
- Finally, 3 months after the intervention/sham was completed participants will return one final time to have all measures repeated to allow for evaluation of activity levels following completion of the intervention.

Retention

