With at least 27 subjects per group (treatment and sham) completing the study and an alpha level of .05, the ANOVA F test will have approximately 97% power to detect a significant main or interaction effect, assuming a large effect size, and a modest degree of correlation among observations from the same individual. A large effect size in this context is one such that the ratio of the standard deviation of the means to the standard deviation of the observations within the populations is at least 0.4.⁷⁷ In addition, the ANOVA F tests will have at least 69% power to detect main effects and 95% power to detect an interaction effect, with alpha set at .05 and at least a medium effect size (i.e., ratio of standard deviation of means to standard deviation of observations within populations is at least 0.25). Given that we expect a large effect between the groups for many outcomes, in addition to the estimated power of at least 95% for the detection of a Group by Time effect in the presence of a medium to large effect, the sample size chosen for this exploratory study will provide sufficient power to detect this significant group differences over time with a high probability; in addition, this study will allow us to more precisely measure expected power in order to plan future studies.

Section 9: Privacy and Confidentiality Issues

Patients' confidentiality will be preserved by coding each data sheet with a unique subject number, and storing the code number key in a locked file cabinet in a locked research office located in the School of Nursing. Protection against breach of confidentiality is provided by training all individuals involved in the research process about the necessity for complete confidentiality, housing all data collected in locked file cabinets in an access-restricted area, and by use of password protected computers and secure servers. Most data are collected using the REDcap system, and any additional files will be stored in Box Health on IU Servers. Although there can be no absolute guarantee of confidentiality, every practical precaution will be taken.

Section 10: Follow-up and Record Retention

Study recruitment will be ongoing. The duration of the entire study is expected to be 18 months, while each participants expected duration is 6 months. The de-identified data will be retained on computer files indefinitely. Hard copy study documents will be kept in a locked, file cabinet in a locked room. Electronic study information will be stored

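### The rule for claiming an NMES effect does not exclude the Time main effect, which compares no arms; confine the claim to the between-arm comparison of change

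*Combined protocol and SAP*

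**What the plan says.** Section 8, Statistical Analysis, sets out one repeated-measures model per outcome: "Each ANOVA model will include the main effects of Time" (baseline, 6 weeks, final visit) and of Group (NMES, sham), plus their interaction. It closes with the only rule for drawing a conclusion: "the significance of the main and interaction effects will indicate the effect of the intervention over time". It adds that "Post-hoc pairwise comparisons of means will be done using Fisher least significant difference procedure", without saying which pairs are meant or which overall test must come first.

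Section 8, Power Considerations, first claims "approximately 97% power to detect a significant main or interaction effect" for a large effect. It then rests the sample size partly on an "estimated power of at least 95% for the detection of a Group by Time effect".

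In Section 2, the Aim 2 hypothesis is that "the amount of daily activity will increase while sitting/lying time will decrease from pre intervention to post intervention time points". Aims 1 and 3 are also worded as improvement, with no comparator. Only Aim 4 names the sham group.

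On change common to both arms, Section 2 states: "It is expected that all patients will benefit from a formalized exercise program regardless of NMES or Sham randomized group". The NMES Protocol Summary in Section 5 makes no distinction by arm: "Participants will be encouraged to begin a formalized exercise plan such as Silver Sneakers", with all measures repeated three months after the intervention.

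**The concern.** The Time main effect averages over the two arms. It asks whether outcomes changed between visits, not whether they changed more on NMES than on sham. The closing sentence nonetheless lists the main effects, without separating Time from Group, among the results that indicate an intervention effect.

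The plan itself expects change in both arms, because everyone is encouraged to exercise before the last visit. The sham arm exists to remove such change from the comparison. A claim resting on Time loses that protection. Section 2 says that these data will support a larger grant application, so a shared trend reported as an NMES effect would carry forward.

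**Working it through.** **Inputs from the documents.** 27 completers per arm (N = 54), m = 3 visits, alpha 0.05, f = 0.25 (medium) and f = 0.4 (large). **Assumed.** Compound symmetry; within-person correlation ρ of 0.3, 0.5 or 0.7 (the plan says only that it is modest); the size of any shared shift or NMES effect, in SD units.

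**1. The plan's own power.** Noncentral F with N·m = 162.
- Group: λ = 162f²/(1 + 2ρ), df 1 and 52.
- Time, and Time by Group: λ = 162f²/(1 − ρ), df 2 and 104.

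| ρ | Group, f = 0.4 (stated 97%) | Group, f = 0.25 (stated at least 69%) | Interaction, f = 0.25 (stated 95%) |
|---|---|---|---|
| 0.30 | 97.7% | 69.5% | 92.9% |
| 0.32 | λ = 25.92/1.64 = 15.80, 97.4% | λ = 10.125/1.64 = 6.17, 68.4% | λ = 10.125/0.68 = 14.89, 93.6% |
| 0.36 | 96.8% | λ = 10.125/1.72 = 5.89, 66.3% | λ = 10.125/0.64 = 15.82, 94.9% |

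The figures reproduce to within two points for ρ of 0.31 to 0.34, so this model is close to the authors'. No single ρ gives both 69% for Group and 95% for the interaction.

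**2. No NMES effect, the same shift s in both arms at both follow-up visits.** The visit means 0, s, s give f² = 2s²/9, so for Time λ = 36s²/(1 − ρ). For s = 0.3, λ = 3.24/0.7 = 4.63, 3.24/0.5 = 6.48 and 3.24/0.3 = 10.8. A shift at the final visit only has the same f² and gives the same results.

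| Shared shift (SD) | Time significant, ρ = 0.3 | ρ = 0.5 | ρ = 0.7 |
|---|---|---|---|
| 0.2 | 22.5% | 30.2% | 47.5% |
| 0.3 | 46.0% | 60.6% | 83.5% |
| 0.4 | 71.7% | 85.9% | 97.9% |
| 0.5 | 89.6% | 97.1% | 99.9% |

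A shared shift adds nothing to the noncentrality of Time by Group, which stays at about 5% (4.8% to 5.2% by simulation).

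**3. No NMES effect and no shift, any of the three tests counted.** 1 − 0.95³ = 14.3%; simulation gives about 14%.

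**4. All three tests required.** With no NMES effect, the false-claim rate is roughly 0.05 × 0.05 × the Time power: 0.0025 × 0.46 = 0.12% up to 0.0025 × 0.999 = 0.25% for shifts of 0.3 to 0.5 SD. Now suppose a real NMES-only difference d = 0.75 SD, lasting over both follow-up visits:
- Interaction: f² = d²/18, so λ = 9d²/(1 − ρ) = 5.0625/(1 − ρ) = 7.23, 10.13, 16.88. Power is 66%, 81% and 96% at ρ = 0.3, 0.5, 0.7.
- Group: f = d/3 = 0.25, because baseline is averaged in. Power is 69%, 60% and 52%.
- All three together (simulation): 30%, 39% and 48%.

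**5. What f = 0.25 means for the interaction.** On this pattern d = 0.25 × √18 = 1.06 SD. At d = 0.5, λ = 2.25/(1 − ρ) = 3.21, 4.5, 7.5, and power is 33%, 45% and 67%.

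**The case against.** The strongest reply is that the sentence is a loose summary. Its stated target is an intervention effect over time, which in this model is the interaction. The design is randomized, blinded and sham-controlled. The power section speaks of an effect between groups and of Group by Time, and it calls the study exploratory. No sentence says that a Time effect alone supports an NMES claim. This stands as evidence of intent. It does not change the rule: the power text justifies a sample size, and the same section also writes of a main **or** interaction effect.

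Secondly, the word joining main and interaction effects can be read as requiring all of them. That reading does keep false claims far below 5%. It would also make the NMES claim depend on Time and on a Group average that includes baseline, with the power loss shown in step 4. The restriction helps under either reading.

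Thirdly, the large percentages depend on assumed shifts. That is correct. Section 2 expects a benefit from exercise but gives no size, and the background says that most patients in exercise trials do not meet the exercise requirements.

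Fourthly, Fisher's procedure in its classical form follows a significant overall test, so within-arm pairs may be gated. The plan does not say so, nor on which test. Gating on Time would not protect the claim; gating on the interaction would.

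A reader might infer that the authors mean to credit shared change to NMES, or that the plan lacks a between-arm test. The documents support neither: the interaction is in every model and has a stated power.

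**Conclusion.** The rule is wrong as written, because it can yield an NMES claim from a test that compares no arms. The logical point needs no assumed number. Its size does: with no NMES effect, 27 per arm and a shared 0.3 SD shift, Time is significant in 46% to 83.5% of trials for ρ of 0.3 to 0.7, against about 5% for the interaction. With no shift at all, counting any of the three tests gives about 14%.

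These are not forecasts of the trial's error rate, although a reader might take them so. They hold under the reading in which any one significant test suffices, and for the assumed shifts. The Group main effect does compare arms and keeps its 5% level; it is a poor basis for the claim because it averages in the pre-treatment visit, and counting it alongside the interaction gives 1 − 0.95² = 9.75%.

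**What to change.** In the last sentence of Statistical Analysis, keep the first half, which gives each outcome its own model. Replace only the clause after it with:

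> *For each continuous outcome, an effect of NMES is claimed only from the between-arm comparison of change, tested by the Time by Group interaction, in the hypothesised direction, and reported as the NMES-minus-sham difference in change from baseline at 6 weeks and at the final visit, with 95% CI. The Time main effect, the Group main effect averaged over visits including baseline, and within-arm pre-post comparisons are descriptive. For Aim 4, the claim rests on the NMES versus sham comparison.*

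Add *compared with sham* to the hypotheses for Aims 1 to 3.

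In Power Considerations, rest the sample size on Time by Group. State the ρ used and the recomputed power: about 93% to 94% for f = 0.25 at ρ of 0.30 to 0.32. The stated 95% needs ρ of about 0.36, where Group power is 66%. Say also that f = 0.25 is a lasting between-arm difference of about 1.06 SD, and that power at 0.5 SD is 33% to 67% for ρ of 0.3 to 0.7.

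The cost is a few sentences, with no new data, visits or patients. The downside is that the stated power looks slightly less favourable. At low ρ the Group test, now descriptive, had similar power (69% against 66% for 0.75 SD at ρ = 0.3).
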